We propose a comprehensive management program for postpartum patients with HDP who are at risk for severe maternal morbidity and mortality. Our program will emphasize three key components: 1) self-monitoring of blood pressures with app-based reporting connected to our electronic health record, 2) blood pressure management directed by a program navigator with guideline and physician support and 3) facilitated transitions of care to primary care clinicians for hypertension management. We will randomize 1400 patients with HDP on postpartum day one with follow up through 3 months postpartum. Primary outcome will be blood pressure control at 2 weeks postpartum. Secondary outcomes include identification and treatment of severe blood pressures, severe maternal morbidity, postpartum and primary care visit attendance, and multiple patient-reported outcome measures. All outcomes will be stratified by race (Black and non-Black) to evaluate disparities and by tight versus usual blood pressure control to evaluate the impact of strict postpartum blood pressure control on outcomes. We hypothesize that a comprehensive postpartum HDP management program will improve hypertension control for all patients and reduce disparities that affect Black patients, and that stricter blood pressure control will be associated with fewer adverse outcomes.

OBJECTIVE

Specific Aim 1: To assess whether augmented remote blood pressure monitoring and tight blood pressure control, both individually and in combination, improve blood pressure control and the frequency of severe hypertension in the first 2 weeks postpartum.

Specific Aim 2: To test whether these interventions narrow the existing Black/non-Black inequity in postpartum outcomes such as blood pressure control and severe hypertension.

ELIGIBILITY CRITERIA

Inclusion Criteria

1. Age ≥ 18 years
2. Diagnosed with a Hypertensive Disorder of Pregnancy (HDP), which includes chronic hypertension, preeclampsia, gestational hypertension, HELLP Syndrome (Hemolysis, Elevated Liver enzymes, Low Platelets), or eclampsia (O10, O11, O13, O14, O15, O16)

Exclusion Criteria

1. Not able or willing to receive electronic surveys
2. Deemed inappropriate for study enrollment by bedside nurse
3. Non-English speaking
4. Discharge on postpartum day 6 or greater
5. Contraindication to ACOG-recommended hypertension control (i.e. chronic kidney disease, stroke)

SCREENING

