- **Interventions:** Participants will be randomized in a 1:1:1:1 ratio in permuted blocks of 4-12 to one of four interventions as summarized in **Table 1** and described in detail below. Randomization will be generated through sealedenvelope.com and allocation through REDCap. Randomization will be stratified by race.

Table 1: Summary of blood pressure (BP) interventions and factorial design

		Postpartum BP Goals	
Interventions		(C) Standard control BP <150/100	(D) Tight control BP <140/90
BP monitoring	(A) OB Provider Monitoring	(#1) Standard control Provider Monitoring	(#2) Tight control Provider Monitoring
	(B) Augmented Remote Monitoring	(#3) Standard control Remote monitoring	(#4) Tight control Remote monitoring

Blood Pressure Care Navigation

(A) *Obstetric Provider Monitoring (In-Person)*: Participants will be instructed to check their blood pressures twice a day for two weeks and daily for weeks 3-6 after delivery and report abnormal blood pressures or symptoms to their obstetric clinicians. Additional postpartum visits beyond the blood pressure check will be directed by their obstetric clinician.

(B) *Augmented Remote Blood Pressure Monitoring*: A physician investigator (fellow or attending) will place an order for "MyHealth BP Flowsheet" in the participant's chart, which triggers the Track My Health feature on MyHealth. The research assistant will demonstrate to the participant how to track blood pressures through the Track My Health feature on the MyHealth smartphone app. Blood pressure monitoring and management plan outlined below. Among women on antihypertensive medication, blood pressure tracking, monitoring, and feedback will continue until care has been transferred to a clinician who can provide long-term care.

Participant and Hypertension Program Manager responsibilities described in detail below:

Table 2. Participant and Hypertension Program Manager Responsibilities

Blood Pressure Monitoring	Participants Responsibilities	Hypertension Program Manager Responsibilities
Weeks 1-2 after delivery	
 ▶ Check blood pressures twice daily ▶ Record BPs every day in MyHealth ▶ Seek urgent care (triage, ED) for sustained severe HTN or symptoms 	
 ▶ Receive BPs notifications daily M-F ▶ Call patients who do not send BPs ▶ Adjust antihypertensive medications based on sections (C) and (D) below

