DBPsevere710_bin	DBP value \geq 110	DBP710 \geq 110	1=yes 0=no
ANYsevere_bin	Any BP value \geq 160/110	SBP710 \geq 160 OR DBP710 \geq 90	1=yes 0=no
dcp_medstart	Any medication started between discharge through week 6 after delivery	n/a	1=yes 0=no
dcpp_medstart	Days postpartum that medication was started	n/a	Continuous
readmit	Hospital readmission	n/a	1=yes 0=no

The two co-primary outcomes are mean systolic blood pressure (SBP) and diastolic blood pressure (DBP) recorded in-office (**Table 3**). In a secondary analysis, we will also include mean blood pressure measurements reported via augmented remote monitoring among women who do not attend in-office visits. The third co-

primary outcome is proportion of participants with sustained severe hypertension during the first 6 weeks postpartum defined as a SBP ≥ 160 or a DBP ≥ 110 on two occasions at least 15 minutes apart.

Secondary Outcomes

We will examine three categories of secondary outcomes (**Table 3**). *Hypertension control and adverse events* includes measures of blood pressure control and events potentially associated with poor blood pressure control such as severe maternal morbidity (SMM) and hospital readmission. Given that our intervention tests different models of care, we will assess *health care utilization* associated with these models including adherence to in-person and remote blood pressure monitoring, medication use, attendance at scheduled visits, and unscheduled visits to an urgent care or emergency room.

Table 3: Study outcomes and time frame for assessment

Hypertension Outcomes		
Blood pressure control (Primary Outcome)	Mean SBP assessed in-office and through all methods	7-10 days
Blood pressure control (Primary Outcome)	Mean DBP assessed in-office and through all methods	7-10 days
Severe hypertension (Primary Outcome)	SBP ≥ 160 or DBP ≥ 110 on two occasions 15 minutes apart and less than 4 hours apart	6 weeks
Hospital readmission	Readmission for hypertension management after delivery discharge	3 weeks
Severe maternal morbidity	Center for Disease Control criteria	6 weeks
Health Care Utilization		
Blood pressure assessment	Proportion who report at least one BP reading post delivery	7-10 days
Medication use	Proportion requiring and/or initiating antihypertensive medications	6 weeks
Urgent care visit	Visit to obstetric triage or an emergency department for hypertension	3 weeks

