APPENDIX J

STANDARD blood pressure control treatment algorithm:

[figure not shown]
V4 Postpartum Hypertension Management Guidelines **STANDARD CONTROL**

Monitoring Frequency

- Weeks 1-2: daily
- Weeks 3+: weekly

How: Seated for 10 minutes, arm at heart level

- If $>150/100$, wait 15 minutes and recheck
- Record second blood pressure

Antihypertensive Medication Escalation Plan:

Nifedipine XL: 30mg daily, 60mg daily, 90mg daily, 120mg daily
Labetalol: 200mg BID, 400mg BID, 600mg TID, 800mg TID
SBP = Systolic Blood Pressure | DBP = Diastolic Blood Pressure

Alert Symptoms:

Headache, visual changes, difficulty breathing, abdominal pain, sudden weight gain

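### The severe-hypertension co-primary names no source of readings, and home readings are captured systematically only in the remote-monitoring arms, so the monitoring comparison mixes effect with detection

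*Combined protocol and SAP*

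**What the plan says.** The Outcomes section sets the third co-primary as the "proportion of participants with sustained severe hypertension during the first 6 weeks postpartum", meaning SBP of at least 160 or DBP of at least 110 on two occasions at least 15 minutes apart. Table 3 adds an upper limit: "on two occasions 15 minutes apart and less than 4 hours apart". Neither place says whether the readings come from the office, obstetric triage, the emergency department, an inpatient stay or the home cuff. The variable derivation table has no entry for this outcome; its severe-pressure variables are built on the 7-10 day values.

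For the other two co-primaries the plan does address source. The text makes them in-office values and brings in "mean blood pressure measurements reported via augmented remote monitoring among women who do not attend in-office visits" only in a secondary analysis. The Table 3 entry is looser ("Mean SBP assessed in-office and through all methods") but still mentions source.

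Under Study Procedures, every participant receives a cuff, and the home measurement schedule is the same in both monitoring arms. What happens to the readings differs:

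- **Remote monitoring (B).** A chart order opens the MyHealth flowsheet. Table 2 gives the participant the task "Record BPs every day in MyHealth", and the program manager calls women who send nothing in weeks 1-2.
- **Provider monitoring (A).** Women are to "report abnormal blood pressures or symptoms to their obstetric clinicians". No study logging of their home values is described.

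All four participant messages (Appendices B to E) ask women to seek care for a sustained severe pair of readings.

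**The concern.** The same home episode has a systematic path into the data in one randomised arm and a participant-initiated path in the other. If the definition is applied as written to whatever is in the record, the opportunity to be counted depends on the monitoring arm. The Aim 1 model reads a negative log-odds ratio as improvement, so extra detection in the remote arms looks like worse control. This could cancel a real benefit of remote monitoring or produce an apparent harm. A larger sample does not help, because the bias does not shrink with N.

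The goal contrast (tight v standard) is much less exposed, because both goals occur within each monitoring arm under the same capture rules.

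**Working it through.** **Inputs from the plan.** Baseline rate 10.2% (Power and Sample Size Considerations; 10% in Table 6). Planned reduction 57%, that is RR 0.43, so 0.102 × 0.43 = 4.39%. Alpha 0.05, power 80%, 250 in standard care v 500 per intervention. With 1:1:1:1 allocation and N = 1000, each monitoring level has 500 and each cell 250. The plan does not state sidedness; I take it as two-sided.

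**The plan's own figure.** The two-proportion sample size for 10.2% v 4.39% at 1:2 allocation, with continuity correction, is 248 in the smaller group against 250 stated. Without the correction, power at 250 v 500 is 84.1%. The stated 57% at 80% power is reproduced and is not in dispute.

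**Detection model (assumed).** Let R be the share of true events captured in the remote arms divided by the share captured in the provider arms. The documents give no value for R. Hold the provider arms at an observed p1 = 0.102. The remote arms are then observed at p2 = 0.102 × (true RR) × R.

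With p̄ the mean of p1 and p2 and n per group:

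- SE0 = √[p̄(1−p̄)·2/n]
- SE1 = √[(p1(1−p1) + p2(1−p2))/n]
- P(significant harm) = Φ[(p2 − p1 − 1.96·SE0)/SE1]
- P(significant benefit) = Φ[(p1 − p2 − 1.96·SE0)/SE1]

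**No true effect.** Example, R = 1.5 and n = 500: p2 = 0.153, SE0 = 0.0211, SE1 = 0.0210, z = (0.051 − 1.96 × 0.0211)/0.0210 ≈ 0.46, Φ = 68%.

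| R | Remote observed | OR | False harm, 500 v 500 | False harm, 250 v 250 |
|---|---|---|---|---|
| 1 | 10.2% | 1.00 | 2.5% | 2.5% |
| 1.10 | 11.2% | 1.11 | 7.5% | 5.6% |
| 1.25 | 12.8% | 1.29 | 24% | 14% |
| 1.5 | 15.3% | 1.59 | 68% | 40% |
| 2 | 20.4% | 2.26 | 99% | 89% |

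The last column matters because the Aim 1 model includes the monitoring-by-goal interaction. With 0/1 coding, the monitoring coefficient compares remote with provider monitoring at the standard goal only, 250 v 250.

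**True 57% reduction.**

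| R | Observed RR (0.43 × R) | Power, 500 v 500 | Power, 250 v 500 |
|---|---|---|---|
| 1 | 0.43 | 94% | 84% |
| 1.25 | 0.54 | 79% | 65% |
| 1.5 | 0.65 | 54% | 42% |
| 2 | 0.86 | 12% | 10% |

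At R = 1/0.43 = 2.33 the observed RR is 1 and the planned effect disappears.

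**With a common source.** If R = 1 and the rate on that source is 10.2%, the plan's sample size stands. If restricting the source lowers the rate, power falls. For the same 57% reduction at 500 v 500, an assumed 8% (v 3.44%) gives z = 1.15 and power 87.5%; an assumed 6% (v 2.58%) gives z = 0.71 and power 76%.

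**The case against.** **Every arm has a route to care.** Provider-arm women are told to report abnormal readings, and the messages to all four arms ask them to seek care for a pair of readings that is essentially the Table 3 event. A reader might infer that provider-arm home readings have no way into the record. The documents do not support that; what differs is systematic capture. This narrows the gap by an unknown amount and does not close it.

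**The team may intend in-facility readings only.** If so, direct capture bias is smaller. The plan does not say it, and an unstated choice can be made after the data are seen.

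**Appendices J and K.** Both say to recheck a high value and "Record second blood pressure". A reader might infer that remote women store only the second value. The word "only" is absent, the appendices are organised by blood pressure goal rather than monitoring arm, and their algorithm figures are not available to this review. The messages to remote women simply ask for daily recording. If only second values were stored, some remote-arm pairs would be lost, which would partly offset the bias. It is an ambiguity to clear up.

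**Interaction and race.** A reader might carry the bias over to the interaction term or to Aim 2. If capture is proportional and equal across goals, the interaction barely moves. Take R = 1.5 and a goal RR of 0.60: cells of 10.2% and 6.12% (provider) and 15.3% and 9.18% (remote) give goal odds ratios of 0.574 and 0.560, a ratio of 0.97. With no goal effect it is exactly 1. The first Aim 2 subgroup is standard care only, where monitoring does not vary, and nothing in the documents shows capture differing by race.

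**Primary status is unsettled.** The Outcomes section also names in-office recording at 7-10 days as the registered primary outcome. That is true, but Table 3 and the Aim 1 analysis still treat severe hypertension as primary.

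**Conclusion.** The concern holds for the monitoring contrast. As written, the co-primary lets ascertainment depend on the randomised monitoring arm, and the bias runs against remote monitoring. Its size cannot be derived from the documents. On the assumptions above (10.2% observed in the provider arms, proportional capture, two-sided 5%), a capture ratio of only 1.25 raises the chance of significant false harm from 2.5% to 24% at 500 v 500, or to 14% for the 250 v 250 coefficient. It also takes power for the planned reduction from 94% to 79% at 500 v 500.

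The documents do not show that false harm will occur, or that the stated power calculation is wrong; that calculation reproduces. It should be settled before analysis, because the outcome cannot be interpreted for one of the two randomised factors until the source is fixed.

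**What to change.** 1. Define the co-primary on readings taken at clinical encounters (office, obstetric triage, emergency department, inpatient) in all four arms, with one abstraction rule. Add a derivation-table entry, and use the same time limits in the text and Table 3.
2. Pre-specify an all-source sensitivity analysis that adds home readings.
3. Pre-specify a second sensitivity analysis on triage, emergency department and inpatient readings only. The Outcomes section expects in-office recording at 7-10 days to vary by monitoring arm, so office readings are not equally available either.
4. Report severe pairs entered in MyHealth separately, within the remote arms.
5. State whether the instruction in Appendices J and K means that both readings of a pair are stored.

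The cost is a definition line, an abstraction rule and two sensitivity analyses. Home-only episodes leave the co-primary, so the event rate and power may fall below those at 10.2%. Clinical-encounter readings reduce differential capture but do not remove it: differences in visit attendance and care-seeking between arms remain and should be stated as a limitation.

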- **Enrollment:** After consenting to the study, participants will receive the initial survey via text web-link or email link. **Survey 1** asks questions about the participant's hypertension history, experience with prenatal care and care at delivery, and socio-demographic questions not reliably obtained from the electronic health record. We estimate that this survey will take 15 minutes to complete. Participants will receive a \$10 gift card for completion.
- **Randomization and Procedures before Hospital Discharge:** All participants will receive an Omron [validated blood pressure monitor](#) with appropriately sized cuff (Appendix A) following measurement of their arm circumference. Many of our patients do not obtain blood pressure cuffs postpartum, and they infrequently are covered by insurance providers. Instructions for blood pressure measurements and discharge instructions will be discussed with the patient and sent via MyHealth messaging with the script described in Appendix B. Participants will be instructed to measure blood pressure after being seated for 10 minutes with legs uncrossed and back supported with their arm positioned at the level of their heart. They will be instructed to avoid caffeine and tobacco for 30 minutes prior to measuring blood pressure. If blood pressures reach a predefined target threshold (Interventions C and D), they should wait 15 minutes and repeat the blood pressure measurement. Participants will be instructed to bring their blood pressure cuff to their first follow up appointment for calibration and clinical correlation. At hospital discharge, participants will receive information regarding follow up after HDP: a) seeking care for sustained severe blood pressures ($\geq 160/110$ mmHg at least 15 minutes apart), b) preeclampsia alert symptoms (headache, confusion, or visual changes), and c) scheduling an appointment with a primary care clinician at 3 months postpartum. All patients will receive a written letter explaining the study (Appendix C) that they can take to clinician visits outside the VUMC system. At discharge, a follow up in-person visit for a blood pressure check within 7-10 days postpartum will be requested by the inpatient team, which is our routine practice. Our specific research interventions are:

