Weeks 3-6 after delivery	
 ▶ Check blood pressures once daily ▶ Record BPs daily in MyHealth ▶ Seek urgent care (triage, ED) for sustained severe HTN or symptoms 	
 ▶ Receive BPs notifications weekly ▶ Adjust antihypertensive medications based on sections (C) and (D) below
Communication with obstetric clinicians		
 ▶ Send updates on HTN management at weeks 2, 4, and 6 ▶ Document medication changes in EStar ▶ Send updates to non-VUMC obstetric clinicians with any antihypertensive medication changes
Care Handoffs	
 ▶ Schedule postpartum visit at 4-6 weeks ▶ Schedule a visit with a primary care clinician or cardiologist at month 3 	
 ▶ Ensure that postpartum visits are scheduled by 4-6 weeks ▶ Ensure that primary care or cardiology visits are scheduled at month 3 ▶ Remind patients about all visits

Blood pressure Control

(C) *Standard Blood Pressure Control*: Blood pressure targets will be <150 mmHg systolic and <100 mmHg diastolic consistent with current postpartum recommendations from ACOG. Blood pressure notifications for the HTN program navigator will reflect these parameters and medications will be initiated or titrated to meet these goals. See Appendix J for specifics on management and Appendix L for recommended medication regimens

(D) *Tight Blood Pressure Control*: Blood pressure targets will be <140 mmHg systolic and <90 mmHg diastolic. Blood pressure notifications for the HTN program navigator will reflect these parameters and medications will be initiated or titrated to meet these goals. See Appendix K for specifics on management and Appendix L for recommended medication regimens.

- ▶ **Survey 2** (6-weeks after delivery): Participants will receive the survey via text web-link or email link. Survey 2 asks questions about the participant's experience managing hypertension after delivery, the Mothers On Respect Index (MORI) and the Communication Assessment Tool geared towards postpartum care, the PROMIS Bank v1.0 Anxiety (adaptive) survey, the PROMIS Bank v1.0 Depression (adaptive) survey, the PROMIS Bank v2.0 Instrumental Support (adaptive) survey. We estimate that this survey will take 20 minutes to complete. Participants will receive a \$20 gift card for completion of this survey.

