- ▶ **Survey 3**: (12-weeks after delivery): Participants will be contacted via SMS text or email to ask about follow up with a primary care physician and chronic hypertension. Participants will receive a \$20 gift card for completion of this survey.

OUTCOMES

Primary Outcomes: The outcome for the R21 and listed on ClinicalTrials.gov is the proportion of patients with a blood pressure recorded in the office at 7-10 days postpartum (**BPinperson**). It is not hypothesized that the primary outcome varies by the blood pressure control intervention but will vary by the blood pressure management intervention.

Secondary Outcomes: We will examine three categories of secondary outcomes (**Table 3**). *Hypertension control and adverse events* includes measures of blood pressure control and events potentially associated with poor blood pressure control such as severe maternal morbidity (SMM) and hospital readmission. Given that our intervention tests different models of care, we will assess *health care utilization* associated with these models including adherence to in-person and remote blood pressure monitoring, medication use, attendance at scheduled visits, and unscheduled visits to an urgent care or emergency room.

We will also examine a variety of *patient-reported outcome measures* especially satisfaction with care. HDP carries not only a risk of long-term health sequelae, but also post-traumatic stress disorder, depression, and anxiety.^{92,93} In a review of patients' experiences with HDP, the potential for worsening or chronic hypertension was associated increased feelings of anxiety and loss of agency.⁹⁴ We hypothesize that augmented remote monitoring and tighter blood pressure control, both individually and in combination, will improve postpartum blood pressure control within the first six weeks postpartum. We also hypothesize that participants, especially Black participants, will find the results of these interventions satisfying and acceptable as they provide a nexus of agency during otherwise stressful life events. Observed reductions in blood pressure provide more frequent and immediate feedback to participants relative to other meaningful outcomes such as SMM or hospital readmission. We also acknowledge the possibility that patients also could find frequent observation of blood pressures and tighter parameters to be burdensome or increase anxiety about health status.

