Postpartum visit attendance	Visit with an obstetric clinician postpartum (excludes acute care visit)	6 weeks
Primary care visit	Visit with a primary care clinician (excludes acute care visit)	12 weeks
Patient-Reported Outcome Measures		
Satisfaction	How satisfied have you been with your postpartum care since discharge? (1-10)	6 weeks
Remote BP monitoring satisfaction	Overall, I am satisfied with my experience with remote blood pressure monitoring	6 weeks
Feeling voice is heard	Overall, my questions and concerns have been listened to since delivery	6 weeks
Mothers on Respect index (MORI)	Assessment of respectful patient-provider interactions and their impact on a person's sense of comfort, behavior, and perceptions of racism or discrimination	6 weeks
PROMIS Emotional Support	16 questions regarding availability to talk to others and feel appreciated by others	6 weeks
PROMIS Self-Efficacy	4 questions about perceived ability to manage difficult or unexpected events	6 weeks
PROMIS depression	Computer adaptive test measuring depression symptoms	6 weeks
Communication Assessment Tool (CAT)	15 questions measuring patient perceptions of clinician interpersonal and communication skills	6 & 15 weeks

SBP=systolic blood pressure | DBP=diastolic blood pressure

We will also examine a variety of *patient-reported outcome measures* especially satisfaction with care. HDP carries not only a risk of long-term health sequelae, but also post-traumatic stress disorder, depression, and anxiety.^{92,93} In a review of patients' experiences with HDP, the potential for worsening or chronic hypertension was associated increased feelings of anxiety and loss of agency.⁹⁴ We hypothesize that augmented remote monitoring and tighter blood pressure control, both individually and in combination, will improve postpartum blood pressure control within the first six weeks postpartum. We also hypothesize that participants, especially Black participants, will find the results of these interventions satisfying and acceptable as they provide a nexus of agency during otherwise stressful life events. Observed reductions in blood pressure provide more frequent and immediate feedback to participants relative to other meaningful outcomes such as SMM or hospital readmission. We also acknowledge the possibility that patients also could find frequent observation of blood pressures and tighter parameters to be burdensome or increase anxiety about health status.

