APPENDIX B: Epic MyHealth Message for Intervention #1 (Standard Control / In-Office Monitoring)

Dear Ms. [last name],

Thank you for being part of the Vanderbilt Fourth Trimester (V4) study. The V4 study will help us learn how to better care for women with high blood pressure in pregnancy.

You have been assigned to the following interventions:

1. Blood pressure goal: <150/100

From discharge through 6 weeks postpartum, we recommend that your blood pressure be less than 150 mmHg systolic (top number) and less than 100 mmHg diastolic (bottom number). If either the top or the bottom blood pressure is higher than the target, your obstetric provider may consider starting or changing medications.

2. Blood pressure monitoring: Obstetric Provider

- You will be given an appointment to have your blood pressure checked in the office within 10 days of delivery. Usually you receive a MyHealth message about the appointment.
- For the first 2 weeks after delivery, you should check your blood pressure twice a day
- For weeks 3 to 6, you should check your blood pressure once a day
- If your blood pressures are over the goal above, contact your obstetric provider

3. Preeclampsia Danger Signs

Seek medical attention within an hour if you have any of the following:

- Blood pressure of 160 mmHg systolic (top number) or 110 mmHg diastolic (bottom number) after two blood pressure checks at least 15 minutes or more apart and within 4 hours
- A persistent headache that does not go away with rest, eating, or Tylenol
- Spots in your vision or difficulty seeing
- Difficulty breathing
- Persistent and worsening pain in your belly especially in the mid-upper or right-upper areas

4. Long-term Care

High blood pressure in pregnancy often goes away after delivery, but in some people it stays. Even if it goes away, having high blood pressure in pregnancy can make you higher risk for high blood pressure or heart disease later in life. You should see a primary care provider or cardiologist within 3 months after delivery to discuss ways to improve your heart health and to monitor your blood pressure. Be sure to tell your provider that you had high blood pressure in pregnancy.

Instructions for checking your blood pressure

1. Wait at least 30 minutes after smoking, eating, drinking caffeine (coffee, tea, soda), or exercising.
2. Sit comfortably at a table with both feet on the floor and your arm resting on the table, palm up.

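### The primary care visit outcome counts only primary care and is assessed at 12 weeks, while the programme hands women off to primary care or cardiology at month 3

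*Combined protocol and SAP*

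**What the plan says.** Under Health Care Utilization, Table 3 lists a primary care visit outcome, defined as a "Visit with a primary care clinician (excludes acute care visit", with a time frame of 12 weeks. Survey 3, described under Study Procedures, is sent 12 weeks after delivery to "ask about follow up with a primary care physician and chronic hypertension".

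The programme text is wider on clinician type. In Table 2 (Care Handoffs), which covers the augmented remote monitoring arms, the participant is to "Schedule a visit with a primary care clinician or cardiologist at month 3" and the programme manager is to "Ensure that primary care or cardiology visits are scheduled at month 3". The manager also reminds patients about all visits. The participant messages for all four arms (Appendices B to E) give the same choice of clinician, but with a deadline: "You should see a primary care provider or cardiologist within 3 months after delivery". The letters to obstetric providers (Appendices F to I) also name either clinician, within 3 months.

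Two places name primary care only. The discharge information for all participants includes "scheduling an appointment with a primary care clinician at 3 months postpartum", and the opening description of the programme lists facilitated transition to primary care clinicians as one of three key components.

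No section says how to code a cardiology visit or a visit booked but not yet held at 12 weeks. None gives a day window for this outcome.

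**The concern.** Transition to long-term care is one of the programme's three components, and this is the Table 3 outcome that measures it. If the outcome is narrower than the handoff being delivered, some women who did what the programme asked will not be recorded as having done so. Two groups are at risk: women whose only long-term visit is with cardiology, and women whose visit takes place after day 84.

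All arms receive the advice, but only the remote arms have a manager who must see that visits are scheduled and who sends reminders. If that work produces additional cardiology visits, or visits at the 3-month mark, the uncounted share may be larger in the remote arms. That would understate the effect of remote monitoring on care transition.

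**Working it through.** **1. Clinician type, side by side**

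| Place | Arms | Primary care | Cardiology |
|---|---|---|---|
| Table 3 outcome | all | counts | not named |
| Survey 3 description | all | asked | not named |
| Table 2, Care Handoffs | remote | accepted | accepted |
| Appendices B to E (participants) | all | accepted | accepted |
| Appendices F to I (providers) | all | accepted | accepted |
| Discharge information | all | named | not named |

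A cardiology-only handoff meets Table 2 and the messages but not the wording of Table 3. This does not depend on how month 3 is read.

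**2. Timing**

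- Outcome and survey: 12 × 7 = 84 days.
- Three calendar months from delivery: 89 to 92 days, depending on the delivery date.
- Gap: 89 − 84 = 5 days to 92 − 84 = 8 days.

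**3. The plan's own power figure**

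Inputs: Table 6 gives 10% baseline attendance and a minimum detectable relative risk of 43%, at alpha 0.05 and 80% power. The power section compares 250 standard-care women with 500 per intervention. For monitoring, those 500 are the two remote cells. Sidedness is not stated; two-sided is assumed.

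Control-group size, with k = 2, d = p1 − p2 and pbar = (p1 + k·p2)/(1 + k):

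n = [1.96·√((1 + 1/k)·pbar·(1 − pbar)) + 0.8416·√(p1(1 − p1) + p2(1 − p2)/k)]² / d²

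With p1 = 0.10, p2 = 0.10 × 0.43 = 0.043 and pbar = 0.186/3 = 0.062:

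- n = (0.5789 + 0.2799)² / 0.057² = 227
- with continuity correction, n = 253, against the stated 250
- without correction, power at 250 vs 500 is 83.4%

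So the 43% reproduces, but as a fall from 10% to 4.3%. Better attendance is a rise. The smallest rise detectable at 250 vs 500 is 10% to 17.6% (RR 1.76), or to 17.9% (RR 1.79) with continuity correction. The direction used in Table 6 is a separate matter; the 17.6% is needed for step 4.

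**4. What uncounted visits would do**

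The miss rates below are assumptions; the documents give none. Start from a true 10% vs 17.6% (unrounded 17.57%), which has 80% power. Recorded rate = true rate × (1 − miss rate).

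| Assumed miss rate | Power, missed equally in both groups | Recorded rates, missed in intervention group only | Power |
|---|---|---|---|
| 10% | 75% | 10% vs 15.8% | 59% |
| 20% | 69% | 10% vs 14.1% | 34% |
| 30% | 62% | 10% vs 12.3% | 14% |

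Equal loss costs some power. One-sided loss costs much more and also biases the estimate, but it is the extreme case, because the provider arms receive the same advice about timing and clinician type.

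**The case against.** The case on the other side is substantial.

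- **12 weeks may simply be the plan's label for 3 months.** Follow-up is described as running through 3 months. The \$50 for finishing all 3 months equals the three survey payments (10 + 20 + 20), the last of which is at 12 weeks. Month 3 can also mean during the third month, and every participant message and provider letter says within 3 months. Many planned visits can therefore fall before day 84. This stands, and it limits the timing part to about a week at most for a visit held by the 3-month date.
- **No coding rule is written.** The variable derivation table has no entry for this outcome, Table 3 names no data source, the Survey 3 items are not reproduced, and the recruiting script says the health record will be reviewed. A late survey response or a record check might capture later visits. This stands: that such visits would not count is a reading of the outcome's wording, not of a stated rule.
- **Primary care only is a legitimate construct.** It matches the component as first described and the discharge information. This stands as a design choice, but it does not match the handoff in Table 2.
- **Neither aim tests care transition,** and this is one of many secondary outcomes. This stands and limits the weight of the point.

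Two stronger readings are tempting. A reader might infer that all women who complete the handoff as planned are coded as failures. The documents do not support that: anyone who sees primary care by week 12 counts, including a woman who also sees cardiology.

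A reader might also infer that a real benefit would appear as harm. That can be constructed: assume true attendance of 20% vs 10%, with remote visits spread evenly over weeks 11 to 15 (1/4 counted, so 5%) and provider visits over weeks 0 to 15 (12/15 counted, so 8%). Nothing in the plan supports that asymmetry. With equal timing the doubling survives: 16% vs 8% for weeks 0 to 15, or 5% vs 2.5% for weeks 11 to 15. If remote visits alone fall evenly in weeks 9 to 13, the result is 15% vs 8%.

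**Conclusion.** The mismatch is in the text and worth correcting. The clinician-type part is firm: Table 3 and the Survey 3 description do not name cardiology, while Table 2 and every participant message accept it. The timing part is conditional: it applies only to visits held after day 84, which includes a visit on the 3-month date itself.

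Any bias in the monitoring comparison would probably be toward no benefit, on the assumption that active scheduling and reminders make cardiology-only or month-3 visits more common in the remote arms. The share of women affected cannot be computed from the documents, so the power figures above show sensitivity, not expected loss. The point concerns the measurement of one secondary outcome. It does not bear on the primary outcomes and does not show that the trial would reach a wrong conclusion.

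**What to change.** - In Table 3, define the outcome identically for all arms as a non-acute visit with a primary care clinician or cardiologist, attended within a stated day window that closes shortly after the 3-month date. About 14 weeks would do: 14 × 7 = 98 days, at least 6 days after the latest 3-month date. A much longer extension is not needed.
- In Survey 3, name both clinician types. Either send it when the window closes or obtain visit dates at that point.
- Cross-check reported visits against the health record in the same way in every arm, and state how visits that are booked but not yet held are coded.
- Report primary care alone by 12 weeks as a supporting result, so that the present measure is kept.
- Reconcile the clinician types and time wording across Table 2, Table 3, Survey 3, the discharge information and the appendices. No change to when visits are scheduled is implied.

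The cost is some wording, one short electronic survey or date query about two weeks later, and possibly slightly more non-response. The 3-month follow-up and payment wording would need a matching edit. Table 3 already lists the communication measure at 15 weeks, so an assessment after 12 weeks is not foreign to the plan.
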